4.7.2 Secondary Measure of Effectiveness

Secondary measures of effectiveness will be determined by evidence and timing of fusion observed in X-rays post-operatively (3, 6, 12, and when available, 24 months).

4.8 Subject Withdrawal

It is recognized that the subject's participation in this trial is entirely voluntary, and that she/he may refuse to participate and may withdraw from participation at any time without jeopardy to any future medical care. It is also recognized that the investigator, at his/her discretion, may withdraw a subject from this study based upon his/her professional judgment.

Other Conditions for Withdrawal:

Any subject who develops a severe concurrent medical illness during the trial should be withdrawn. This type of illness is defined as any illness that would hinder the subject's ability to return for scheduled follow-up appointments. Such a withdrawal will not be counted for the purposes of determining success or failure.

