3 TRIAL DESIGN

3.1 Design

The randomized controlled trial will prospectively evaluate the safety and efficacy of the Nexxt Matrixx[™] System titanium implant supplemented with a pedicle screw system as compared to a representative PEEK cage currently used in routine fashion for lumbar interbody fusion procedures. This study will capture clinical and radiographic outcomes on patients up to 2 years post operatively. Both cages will be used in conjunction with milled local autograft bone generated as part of the spinal fusion procedure (no iliac crest autograft will be utilized).

This single centered study will enroll up to 70 subjects (n = 35 per group), with subjects followed for a minimum of 12 months post-surgery. All subjects enrolled in the study will be recruited from a pool of subjects eligible for combined interbody/posterolateral lumbar fusion surgery. The inclusion/exclusion criteria are listed below.

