5 COMPLICATIONS

In addition to the standard operating procedures for reporting complications per hospital/physician protocol, all clinical events, including both observed or volunteered problems, complaints, symptoms, physical signs or disease which either occur during the study, having been absent at baseline, or, if present at baseline, appear to worsen during the clinical outcomes collection study are to be recorded as complications in the subject's medical record and on the appropriate case report form.

Complications reported in the literature as most commonly associated with interbody and posterolateral lumbar fusion procedures include, but are not limited to, infection, nerve damage, blood clots, blood loss, and bowel and bladder problems, along with complications associated with anesthesia. A potential risk inherent to spinal fusion is failure of the vertebral bone and graft to properly fuse, a condition that may require additional surgery.

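### Section 4.8 withdraws subjects too ill to attend visits, and no provision is made for collecting their later safety outcomes

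*Combined protocol and SAP*

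**What the plan says.** Section 4.8 (Subject Withdrawal) gives three routes out of the study: the subject's own choice, the investigator's discretion (the investigator "may withdraw a subject from this study based upon his/her professional judgment"), and illness. On illness it says: "Any subject who develops a severe concurrent medical illness during the trial should be withdrawn". The definition follows: "This type of illness is defined as any illness that would hinder the subject's ability to return for scheduled follow-up appointments". The only consequence stated is: "Such a withdrawal will not be counted for the purposes of determining success or failure". Success and failure are fusion terms here (Sections 4.6 and 4.7.1). The section is silent on safety data after withdrawal.

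Section 5 (Complications) asks for the recording of "all clinical events, including both observed or volunteered problems, complaints, symptoms, physical signs or disease which either occur during the study", in both the medical record and the case report form. It lists the complications most often linked to these operations, including "infection, nerve damage, blood clots, blood loss, and bowel and bladder problems".

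Section 4.5 (Follow-Up Assessments) places the review of adverse events since discharge, neurological status and device integrity at the 3-, 6- and 12-month visits, with 24 months optional.

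Section 3.1 (Design) names safety alongside efficacy as what the trial evaluates. It plans up to 70 subjects, 35 per group, "with subjects followed for a minimum of 12 months post-surgery".

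**The concern.** The trigger for withdrawal is inability to attend, not refusal of further follow-up. The definition covers any illness, so a severe infection, clot or nerve injury arising from the operation can meet it. Such a subject leaves a study whose safety information after discharge is gathered at visits. The plan describes no telephone contact, chart review or other collection for someone who has left.

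At stake is what happens next to that subject: whether the illness resolved, whether the operated levels were reoperated, whether hardware failed, whether the subject died. Missed visits do not make this information unobtainable, because much of it can be learned by telephone or from the medical record. Observation would end for a reason related to the outcome being watched, which is informative censoring. With 35 subjects per arm, a few unrecorded reoperations or deaths would matter to any description of safety.

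**Working it through.** **Step 1: read the sections together.**

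| Question | Where | Answer |
|---|---|---|
| Who is withdrawn for illness? | 4.8 | Anyone whose illness hinders return visits, whatever its cause |
| Is the triggering illness recorded? | 5 | Yes, on the case report form, as an event during the study |
| How are post-discharge safety data gathered? | 4.5 | At the scheduled visits |
| Does collection continue after withdrawal? | 4.5, 4.8, 5 | Not stated |

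Section 6 is a useful contrast. If enrollment closes early, it says expressly that subjects already enrolled are followed up to 12 months. Section 4.8 has no equivalent sentence for ill subjects.

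The exposed data are therefore the outcome of the triggering illness and all later events. Events up to and including the trigger are not exposed.

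**Step 2: size under assumed inputs.** The only usable figure in the documents is the planned enrolment, 2 x 35 = 70. There are no complication, withdrawal or dropout rates. The following inputs are assumptions:

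- w, share withdrawn for illness: 2% to 10%
- p, later event rate in everyone else: 5% to 20%
- RR, relative risk of a later event in withdrawn subjects: 1 to 4
- no event after withdrawal is seen

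Formulas:

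- true rate = (1 - w) x p + w x p x RR
- rate seen, all subjects in the denominator = (1 - w) x p
- rate seen, only non-withdrawn subjects in the denominator = p
- events missed = 70 x w x p x RR

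| Case | w | p | RR | Events missed | True rate | Seen, all 70 | Seen, not withdrawn |
|---|---|---|---|---|---|---|---|
| Low | 0.02 | 0.05 | 1 | 70 x 0.02 x 0.05 x 1 = 0.07 | 5.0% | 4.9% | 5.0% |
| Middle | 0.05 | 0.10 | 2 | 70 x 0.05 x 0.10 x 2 = 0.7 | 9.5% + 1.0% = 10.5% | 9.5% | 10.0% |
| High | 0.10 | 0.20 | 4 | 70 x 0.10 x 0.20 x 4 = 5.6 | 18% + 8% = 26% | 18% | 20% |

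With all 70 in the denominator, the rate seen is always too low, by 0.1 to 8 percentage points. With only non-withdrawn subjects in the denominator, the shortfall is zero when RR = 1 and reaches 26% - 20% = 6 points in the high case.

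**Step 3: between the cages.** If w, p and RR are the same in both arms, the expected loss is the same in both. In the middle case it is 35 x 0.05 x 0.10 x 2 = 0.35 events per arm. A difference arises only if withdrawal or risk differs. For example, assume 4 severe complications in one arm and 1 in the other, all withdrawn at onset, each with a 50% chance of later revision or death. The expected losses are then 4 x 0.5 = 2.0 and 1 x 0.5 = 0.5. The 4 and the 1 themselves would still be on record under Section 5.

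**The case against.** The best defence is that Section 4.8 does not order safety collection to stop. It states one consequence, for the fusion count, and Section 5 already requires every clinical event during the study to be entered on the case report form. The word concurrent suggests unrelated disease, and the instruction is phrased as should, not must. Sections 4.7 and 6 define no safety endpoint or safety analysis, so no planned comparison is shown to be distorted. The content of the case report forms in Appendix 1 is not in the text reviewed, so an end-of-study form may exist.

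Much of this stands, and it rules out several stronger readings that a reader might infer:

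- **That the plan orders safety follow-up to end.** This would be drawn from silence. It is a natural reading where collection depends on visits, but it is not a stated rule.
- **That the serious complication itself disappears.** Section 5 requires it to be recorded.
- **That the withdrawn subjects are those most likely to have had a serious surgical complication.** The definition allows overlap, but the documents do not show how much.
- **That a difference between cages is diluted.** This needs withdrawal or risk to differ by arm, for which the documents give no evidence.
- **That Section 3.1 is contradicted.** Its 12-month minimum is a planned duration, and any withdrawal provision, including the voluntary one, shortens follow-up for some subjects.

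The defence leaves one gap. Section 5 covers events that occur during the study, and nothing says whether that duty continues for a subject who has been withdrawn. The definition in Section 4.8 governs over the connotation of concurrent, and it has no exemption for surgical or device-related illness.

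**Conclusion.** The concern holds as a gap in data collection. Followed as written, the plan can lose the outcome of the triggering illness and later events in subjects who leave because they are ill, although safety is a stated aim. It does not lose the triggering event.

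The size cannot be derived from the documents. The range of about 0.07 to 5.6 missed events among 70 subjects, with a middle case of 0.7, rests wholly on the assumed inputs and on no event being captured after withdrawal. Under-reporting is certain in direction for event counts and for rates over all 70 whenever a later event goes unseen. For rates among subjects not withdrawn, it also requires a higher later risk in those withdrawn. No bias between the cages is shown. The exclusion of these subjects from the fusion count is a separate matter.

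The change is worth making because it is cheap and because events not collected at the time may not be recoverable later.

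**What to change.** Amend Section 4.8 to separate missed visits from the end of data collection:

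- A subject who cannot attend because of illness stays in the study for data collection, and the visits concerned are marked missed.
- At 3, 6 and 12 months the site collects, by telephone and medical-record review, complications (including the outcome of the triggering illness), reoperation at the operated levels, hardware failure and vital status. This continues unless the subject withdraws consent to it.
- The provision for withdrawal at the investigator's discretion stays as it is.
- Sections 4.5, 4.8 and 5 are reconciled, so that each says the same about which safety data are collected from a subject who no longer attends.

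This concerns data collection only and changes nothing in clinical care. The cost is a protocol amendment, a check that the consent covers record review, and a few calls or chart reviews at a single centre. Under the assumed 2-10%, that means about 70 x 0.02 = 1.4 to 70 x 0.10 = 7 subjects.

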4.2 Randomization

All subjects will be randomized in the trial to receive either the Nexxt Spine Nexxt MatrixxTM 3D-printed titanium cage or the HonourTM PEEK cage supplemented with a pedicle screw system and milled local autograft bone. Subject randomization will be stratified according to smoking status. Subjects will be blinded to their group status for the duration of the study assessments and procedures (12 months post-operatively).

4.3 **Perioperative and Postoperative Management**

Surgeons will perform combined interbody and posterolateral lumbar fusion utilizing either Nexxt MatrixxTM or PEEK cages supplemented with a pedicle screw system cleared for fusion and milled local autograft bone (per customary protocol).

Data will be collected during and immediately after the surgery according to the parameters described by the Nexxt Matrixx[™] IF/PLF CRFs. This includes: diagnosis, duration of surgery, blood loss, OR time, length of hospital stay, instrumentation used, type of procedure, and surgical level(s). In addition, all intra-operative complications (e.g. excessive blood loss, hematoma, vascular injury, etc.) will be reported and recorded as a complication on the CRF.

Intra-operative (after hardware installation is completed) or immediate postoperative x-rays will be obtained. Postoperative care will follow the standard of care at each institution for subjects who undergo fusion procedures.

Postoperative care is extremely important. The subject should be warned that noncompliance with postoperative instructions could lead to breakage of the pedicle screw system and/or possible migration requiring revision surgery to remove the pedicle screw system.

Screening/	Procedure	3 months	6 months	12 months	24 months
Enrollment		(± 7 days)	(± 14 days)	(± 30 days)	(± 60 days)
procedure)					
Х					
Х					
Х					
Х	Х	Х	Х	Х	X**
	Х				
Х		Х	Х	Х	X**
X		Х	X	Х	X**
X		Х	X	Х	X**
			X*		
Х	Х	Х	Х	Х	X**
	Enrollment (-60 days of procedure) X X X X X X X X X X X X	Enrollment (-60 days of procedure) X X X X X X X X X X X X X X X	Enrollment (-60 days of procedure)(± 7 days)X	Enrollment (-60 days of procedure)(± 7 days)(± 14 days)XXX	Enrollment (-60 days of procedure) $(\pm 7 days)$ $(\pm 14 days)$ $(\pm 30 days)$ X </td

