4.5 Follow-Up Assessments

Subjects will be asked to return postoperatively at 3 months (\pm 1 week), 6 months (\pm 2 weeks), and 12 months (\pm 1 month) for a clinical and radiographic exam. An additional visit at 24 months may be scheduled at the request of either the physician or the subject. The following data will be recorded on the Case Report

Forms (CRFs) and in addition, electronic data entry will be employed via an Internet connection when possible using REDCap.

Clinical assessment: The investigator will carry out a clinical examination at the 3, 6, 12, and when available, 24-month visits to assess:

- subject compliance with postoperative care instructions,
- ability to return to work and normal activity, and
- any procedure related or device related adverse events since discharge from the hospital
- review of medication usage
- progress towards fusion consolidation
- Neurological status All subjects' neurological status will be assessed and recorded as intact or not intact, based upon the investigator's motor, sensory and reflex evaluations.

Subject self-assessment (Patient completed forms):

• Each subject will be asked to complete a follow-up Oswestry Disability Index (ODI) form and a Back and Leg Pain VAS form at each follow-up visit.

Radiographic assessment: Each subject will undergo AP, lateral and flexion/extension radiographs at the 3, 6, 12, and when available, 24-month visits as well as a CT scan at 6 months to assess:

• integrity of the device and graft, with observation for events such as rod, hook, screw and/or spacer (if applicable) migration or subsidence, hardware fracture, and progress towards fusion consolidation

Findings from any additional imaging studies deemed necessary by the investigator will be recorded and reported with study results.

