4.7 Success Criteria

4.7.1 **Primary Measure of Effectiveness**

A subject will be considered a success if fusion is a Grade BSF-3 at 6 months. The primary outcome measure of effectiveness will be determined by the fusion rate at 6 months post-operatively in subjects implanted with either titanium cage as compared to the PEEK cage.

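### Section 4.8 does not make clear which subjects withdrawn for illness leave the primary fusion count, and one reading discards 6-month results already obtained

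*Combined protocol and SAP*

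**What the plan says.** Section 4.8 (Subject Withdrawal) describes three ways out of the trial.

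- **Subject's choice.** A subject "may withdraw from participation at any time without jeopardy to any future medical care". No counting rule is given.
- **Investigator's discretion.** The investigator "may withdraw a subject from this study based upon his/her professional judgment". No counting rule is given.
- **Illness.** "Any subject who develops a severe concurrent medical illness during the trial should be withdrawn". The definition is broad: "This type of illness is defined as any illness that would hinder" attendance at follow-up. This is the only route with an analysis consequence: "Such a withdrawal will not be counted for the purposes of determining success or failure".

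Section 4.7.1 sets the endpoint without reference to withdrawal: "A subject will be considered a success if fusion is a Grade BSF-3 at 6 months". It compares fusion rates among subjects who received each cage. Section 4.6 defines radiographic failure as BSF-1 or BSF-2, so a subject with no grade is neither a success nor a failure.

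Section 4.2 states blinding for subjects only: "Subjects will be blinded to their group status for the duration of the study assessments and procedures". Section 6 names no analysis population, no method for missing outcomes and no sensitivity analysis.

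**The concern.** The illness rule is a counting rule triggered by something that happens after randomisation and surgery. Two features stand out.

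**Timing.** The rule applies throughout the trial. Follow-up lasts at least 12 months (section 3.1), while the primary outcome is fixed at 6. A subject who falls ill at month 9 may already have a gradable 6-month CT, and the text does not say whether that grade stands.

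**Scope.** The definition turns on whether the illness hinders visits. The word 'concurrent' may hint at unrelated illness, but the definition does not require it. Section 5 lists infection, nerve damage and blood clots among the recognised complications of these operations, and a severe case could meet the definition.

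At stake is the denominator of the primary comparison. If it is settled only once the data are in, the choice is open to the suspicion that the result guided it. If exclusions fall unequally and relate to fusion, the comparison is also biased.

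**Working it through.** **1. The three readings of the sentence in 4.8**

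| Reading | Ill at month 9, 6-month CT done | Ill at month 4, no 6-month CT |
|---|---|---|
| (a) The subject leaves the count | Grade discarded | Left out |
| (b) Only subjects without a 6-month CT leave | Grade used | Left out |
| (c) The withdrawal event is not scored; any grade is kept | Grade used | Not settled |

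Section 4.7.1 read alone favours (b) or (c). The words of 4.8 allow (a). No other section decides between them.

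**2. Inputs for size**

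From the documents: 35 per group (section 3.1). The documents give no fusion rate, withdrawal rate, significance level or test, so there is no planned figure to reproduce. Assumed here: equal true fusion p in both arms (70% or 80%), two-sided 5%, and uncorrected chi-square or Fisher's exact test.

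**3. Bias**

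If one arm loses a fraction f of its failures and g of its successes, and the other arm loses none:

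bias = p(1−g) / [p(1−g) + (1−p)(1−f)] − p

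With p = 0.70 and g = 0:
- f = 0.10: 0.70/0.97 − 0.70 = 2.2 points
- f = 0.20: 0.70/0.94 − 0.70 = 4.5 points
- f = 0.30: 0.70/0.91 − 0.70 = 6.9 points

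The expected number of failures is 35 × 0.30 = 10.5, so these are losses of about 1, 2 and 3 subjects.

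With p = 0.80 and g = 0: 0.80/0.98, 0.80/0.96 and 0.80/0.94, each minus 0.80, give 1.6, 3.3 and 5.1 points.

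Mixed case (f = 0.20, g = 0.10): 0.63/0.87 − 0.70 = 2.4 points, and 0.72/0.88 − 0.80 = 1.8 points.

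**4. Type I error**

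Exact enumeration, each subject classed as fused, not fused or dropped:

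| Loss | 70%: chi-square / Fisher | 80%: chi-square / Fisher |
|---|---|---|
| None | 5.1% / 2.8% | 4.9% / 2.5% |
| 10% of one arm's failures | 5.6% / 3.6% | 5.4% / 3.1% |
| 20% of one arm's failures | 7.2% / 5.0% | 6.5% / 4.1% |
| 30% of one arm's failures | 9.9% / 7.3% | 8.3% / 5.6% |
| Mixed, one arm | 5.7% / 4.0% | 5.4% / 3.6% |
| 10-30% of failures, both arms | 5.2-5.3% / 3.3% | 5.1-5.2% / 2.9-3.0% |
| 10-20% of one arm, regardless of fusion | 5.2-5.3% / 3.6% | 5.1-5.2% / 3.3-3.4% |

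Bias is zero in the last two rows.

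**5. Handling alone can move a result**

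Assume 4 titanium and 1 PEEK subjects have no 6-month grade. Leaving them out gives, say, 26/31 against 20/34 fused: +25.0 points, Fisher p = 0.032. Counting them as not fused gives 26/35 against 20/35: +17.1 points, p = 0.21. The extreme imputations give +14.3 points (26/35 against 21/35, p = 0.31) and +28.6 points (30/35 against 20/35, p = 0.016).

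**The case against.** **The sentence may be harmless.** Its grammatical subject is the withdrawal, not the person, and section 4.7.1 sets success at 6 months unconditionally. A reader might infer that the plan definitely throws away CT grades already obtained. The documents do not say so; reading (a) is only one possibility. What stands is that nothing rules it out.

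**Selection by an unblinded investigator.** A reader might infer that an unblinded investigator decides which ill subjects leave the count. Section 4.8 names no one as judge of the illness, and investigator discretion is a separate route. Primary grades are read independently after data collection ends (section 4.6), so they cannot drive withdrawal. What remains is narrower: only subjects are stated to be blinded, and the investigator follows "progress towards fusion consolidation" at each visit (section 4.5). Late reading protects the grade, not the decision on who stays in.

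**The harm is assumed.** The larger figures come from dropping only failures from only one arm, a severe mechanism for illness that hinders attendance. Fisher's test exceeds 5% only at the 30% loss, and the mixed case is mild. This is correct and limits the point to possible harm.

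**There is a rule for illness.** It would be too strong to say that no withdrawn subject has a counting rule. Illness has one, though unclear; the other two routes have none.

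**Conclusion.** The point holds as an unclear counting rule in the primary analysis that can, on one reading, remove valid 6-month outcomes because of a post-randomisation event. It should be fixed. It is not evidence that the comparison is biased.

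On the assumptions above, with no true difference, bias runs from zero (losses equal, or unrelated to fusion) to about 7 points (30% of one arm's failures lost at 70% fusion). Type I error in that last case is 9.9% with chi-square or 7.3% with Fisher. Direction and actual size cannot be derived, because the documents give no withdrawal or fusion rates. Confidence is high that the wording needs repair, and low that it would change the result materially.

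**What to change.** **Section 4.8.** Replace the last sentence with: *The primary analysis includes all randomised subjects who were implanted, in the group assigned; every 6-month CT obtained is graded and used, whether or not the subject is later withdrawn for any reason.*

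**Section 4.7.1.** It already refers to implanted subjects. Align it by stating that subjects randomised but never implanted are reported by arm.

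**Section 6.** Count an implanted subject with no 6-month CT as not fused in the primary analysis, whatever the type of withdrawal. Add two sensitivity analyses: available cases, and best/worst case. Report withdrawals by arm, reason and timing.

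**Cost.** Wording and a little more analysis; no extra subjects, visits or scans, and no change to the clinical rule on who is withdrawn. Fusion rates may look slightly lower. Scoring missing as not fused is not neutral either: each missing subject who would have fused lowers that arm's rate by 1/35 = 2.9 points, which matters if missing CTs are unequal between arms. That is why the sensitivity analyses are needed. Best/worst-case limits widen by the same 2.9 points per missing subject; two missing in each arm give 4/35 = 11.4 points, too wide to serve as the primary analysis.
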